2.0 Background

2.1 Scientific Background and Gaps

Describe the scientific background and gaps in current knowledge.

For clinical research studies being conducted at Penn State Health/Penn State College of Medicine, and for other non-PSH locations as applicable, describe the treatment/procedure that is considered standard of care (i.e., indicate how patients would be treated in non-investigational setting); and if applicable, indicate if the treatment, drug, or device is available to patient without taking part in the study.

Behavioral and psychological symptoms of dementia (BPSD) is significant in persons with dementia living in nursing homes. Evidence suggests that up to 90% of persons with dementia experience at least one BPSD. Agitation includes various disruptive behaviors, including verbal and physical, aggressive and non-aggressive behaviors, such as screaming, wandering, resisting, grabbing, and hitting. Among the BPSDs, agitation is the most challenging symptom. Agitation occurs in 90% of nursing home residents with dementia. Medications are commonly used as a treatment for agitation but show limited effect and have significant side effects. Non-pharmacological interventions are recommended as the first-line treatment, but most are labor-intensive and show mixed effects. Thus, identifying feasible and effective non-pharmacological interventions to reduce agitation is critical.

Researchers have tested the association between lighting and BPSD, especially agitation and depression. Evidence has shown that circadian disruption, short daylight exposure, and changes in interior daylight conditions are related to agitation. Light is the strongest external stimuli regulating the circadian rhythm, but older adults are at a higher risk for circadian disturbances and need more and brighter light to regulate their circadian rhythm because of reduced suprachiasmatic nuclei (SCN) activity and age-related vision deficiencies. In addition, persons with dementia living in nursing homes do not have sufficient daylight exposure to maintain a stable circadian rhythm. Evidence also shows that many nursing homes are too dim during the day. Therefore, ambient lighting is promising in reducing agitation in dementia, especially for older adults living in nursing home s.

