5.6.2.3 Assent of Adults Unable to Consent

Describe the process for assent of the subjects. Indicate whether assent will be required of all, some, or none of the subjects. If some, indicate which subjects will be required to assent and which will not.

If assent will not be obtained from some or all subjects, provide an explanation of why not.

Describe whether assent of the subjects will be documented and the process to document assent. The IRB allows the person obtaining assent to document assent on the consent document and does not routinely require assent documents and does not routinely require subjects to sign assent documents.

Affirmative assent will not be obtained for this study. In my experience, when people with dementia are not capable of providing consent, that usually means that their cognitive function is too impaired to have a good understanding of the research (e.g., purposes and procedures). In that case, they would not be able to provide a meaningful assent either. Thus, in this study, when the residents cannot provide consent, we will not ask for their assent.

Alternatively, when we interact with them and conduct research procedures, such as asking questions for cognitive assessment and putting on the lighting monitor, we will ask their permission and observe their verbal response and non-verbal behavioral cues. When the resident verbally agrees or does not show observable resistance for the monitor. If they express observable verbal or non-verbal resistance to the procedures, such as stating "go away" "I don't want that" or push away the monitor, we will not proceed with the procedures and may approach the resident at a later time.

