7.1 Study Design

Describe and explain the study design.

Aim 1: Pilot test the effect of SABL in reducing agitation in persons with dementia. This is a crossover, cluster randomized control trial to pilot test the effect of SABL in NHs. This design includes a 4-week intervention period and 2-week washout period. This design will allow for participants to act as their own control and thus reduce the needed sample size and strengthen the research rigor. The study procedures include five phases over 13 weeks. We will recruit a total sample of 40 nursing home residents with dementia and agitation from the 2 nursing homes, 20 residents from each nursing home. The two NHs will be randomly assigned into different sequences for intervention and control. Otherwise, the same study procedures will be

conducted simultaneously at the two NHs. During the daytime, participants will be guided and encouraged to spend time in the designated areas in the dining room and activity room for their meals and daily activities. For blinding prior to control period, we will perform installation procedures with non-SABL light bulbs. We will evaluate the effect of SABL on agitation, other BPSD, affect, and sleep, based on the actual lighting levels participants receive measured by personal light monitors. The study procedures include five phases: 1) baseline, 2) intervention, 3) post intervention/washout, 4) control, and 5) post control/washout. The sequence of intervention and control differs between the two NHs based on randomized assignment. Agitation and lighting will be measured at baseline and then once every two weeks throughout the study. We hypothesize that participants will show less agitation during and after SABL compared to baseline and control periods. We will also explore the intervention effect on other BPSD and affect and monitor adverse effects. **Aim 2: Evaluate the fidelity of the SABL delivery.** We will evaluate the fidelity of SABL delivery by measuring lighting intensity (lux) and CS levels in two ways: 1) on-site light measurements, and 2) a personal light monitor. The actual lighting data will be compared to the intended SABL design.

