- 1) Data extraction from CMS Nursing Home Compare Website (<https://www.medicare.gov/care-compare/>): Data on facility characteristics, including number of certified beds, ownership, quality rating, participation in Medicaid, staffing, COVID-related data is publicly available and can be accessed through the link provided above.
- 2) Chart reviews: Data on resident characteristics, including age, race, sex, diagnoses, level of cognitive impairment, current medication use, current listed comorbidity and physical function, BPSD in the past two weeks, pain in the past two weeks, current vision status, current hearing status, and other clinical conditions.
- 3) Surveys based on staff caregivers' reports: The surveys will be conducted on paper and in-person with researcher administering the survey to the staff caregiver for proxy report of residents' dementia stage, agitation, other BPSD, affect, and side effects.
- 4) Personal light monitor, LYS button, placed on individual resident participants to measure lighting intensity (lux) and CS levels participants receive.

There will be seven visits for data collection throughout the 13-week of the study: baseline visit (week 1) and six follow-up visits, every other week (weeks 3, 5, 7, 9, 11, 13). The procedures for each visit are as follows:

Baseline visit: Procedures 1 through 4.

Follow-up visits: Procedures 3 and 4.

For the procedure 4, the light monitor will be worn 7 days a week during the data collection weeks (week 1, 3, 5, 7, 9, 11, & 13).

Aim 2: We will evaluate the fidelity of SABL delivery by measuring lighting intensity (lux) and CS levels.

Data collection procedures will include the following:

- 1) on-site manual light measurements
- 2) personal light monitor, LYS button, placed on individual resident participants (same as the procedure 4 in aim 1).

The procedures will be conducted primarily on site at the nursing home facilities.

The procedure 1 will be conducted twice a week throughout the 13-week study period.

For the procedure 2, as mentioned in aim 1, the light monitor will be worn 7 days a week during the data collection weeks (week 1, 3, 5, 7, 9, 11, & 13).

Aim 3: Staff and Administrators

Data collection methods include the following:

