We will evaluate resident participants' baseline agitation, BPSD, affect, and sleep, based on the residents' staff caregivers' inputs and observations of the residents. We will assess agitation, BPSD, affect, and sleep using the Cohen-Mansfield Agitation Inventory (CMAI), Neuropsychiatric Inventory-Nursing Home version (NPI-NH), Philadelphia Geriatric Center Affect Rating Scale (ARS), and Pittsburgh Sleep Quality Index (PSQI), respectively,

We will measure lighting level by 1) on-site manual light, and 2) a personal light monitor, LYS button during the baseline week. The LYS button is small (1 inch), light weighted (4g), and user friendly. It has a clip at the back of the button and can be easily clipped on clothes. For a resident who does not mind having the sensor placed on clothing, we may place it on the shirt collar or shoulder. We will communicate with their caregivers so that

they are aware of the button when clothes are being changed and make sure the button is clipped back on. We will check the device on site at least twice per week and will retrieve data after each week of data collection. We will pre-set a series of algorithms determining the device use status. If the device appears not to be placed or functioning properly, the system will send a warning message to the team and we will make all attempts to check the device on site. We will manually measure light level twice a week during the baseline week. In addition, we will place a personal light monitor, LYS button, on participants, all day, 7 days a week, during the baseline week.

Aim 3: Staff and administrators

1. Screening survey: We will ask participants to fill out the survey to confirm their eligibility. If they are eligible, we will continue to the next steps.
2. Baseline survey: we will ask participants to fill out a survey to collect data about their demographics and relevant work experiences (e.g., age, race, gender, education, and professional experiences).
3. Feasibility surveys: we will ask participants to fill out the Acceptability of Intervention Measure (AIM), Feasibility of Intervention Measure (FIM), and Intervention Appropriateness Measure (AIM) to evaluate the acceptability, appropriateness, and appropriateness of the SABL intervention.
4. Qualitative interview: their evaluation on the acceptability, feasibility, and appropriateness of the SABL lighting intervention.

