7.4.24 Subject Compliance Monitoring

Insert the procedures for monitoring subject compliance.

Each participant will wear the personal light monitor, LYS Button (Figure) to measure lighting intensity (lux) and CS level received. The data will be used to further calculate participants' hours of intervention exposure per day.

Lighting will be measured once every 10 minutes, all day, 7 days a week, every other week over the 13-week study period. The monitor is small (1 inch), lightweight (4g), and user-friendly and will be placed on participants' shirt collar or shoulder.

Figure . Light Monitor LYS Button

In addition, the light monitor enables real-time remote checking. [name] will pre-set a series of algorithms determining the device use status. If the device appears not to be placed or functioning properly (e.g., lighting data remains completely unchanged for over 1 hour during daytime), the system will send a warning message to the team (including [name] and [name]). We will make all attempts to check the device on site.

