8.0 Number of Subjects and Statistical Plan

8.1

Number of Subjects

Indicate the maximum number of subjects to be accrued/enrolled, to include all persons who sign consent for the study. If applicable, distinguish between the number of subjects who are expected to be enrolled and screened, and the number of subjects needed to complete the research procedures (i.e., numbers of subjects excluding screen failures.)

Aims 1 and 2: Residents

Resident: The target sample size is 40 nursing home residents. We expect to screen 80 potential residents to identify and enroll 40 eligible residents.

Aim 3: Staff and Administrators

Staff: We plan to enroll 16 NH staff/administrators, including three CNAs, one activity staff, one nurse, one DON, one DOM, and one NHA.

8.2

Sample Size Determination

If applicable, provide a justification of the sample size outlined in section 8.1 to include reflections on, or calculations of, the power of the study.

Aims 1 and 2: Residents

We will recruit 40 residents with ADRD and agitation, 20 from each NH. The two NHs have at least a floor or a wing that is primarily dedicated to residents with ADRD, where we plan to

install the lighting and carry out the study. As attrition is expected to be around 10%, based on prior studies with a similar population, this will result in a final sample size of 36. This sample size was calculated based on a significance level of $\alpha=.05$, medium effect size Cohen's $d=0.53$, reported in previous studies, power=0.92.

Aim 3: Staff and Administrators

CNAs, activity staff, and nurses provide the most direct care. Priority will be given to individuals who provide care for resident participants. DONs, DOMs, and NHAs are decision makers for intervention implementation. The DOMs can provide feedback on the feasibility of installing and maintaining the lighting system and ensure the installation follows NH regulations.

Potential participants will be initially identified by NH staff and confirmed by the research team. Sample size may be increased to reach data saturation.

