8.3 Statistical or Analytic Methods

Describe the statistical methods (or non-statistical methods of analysis) that will be employed.

Aim 1

All data will initially be assessed with descriptive techniques to determine distributions and identify outliers. Baseline to post-intervention changes in participants' CMAI, NPI-NH, and ARS scores will be used as the outcomes in all subsequent analyses. To conduct the group analysis, each participant will serve as their own control, which allows minimal use of control variables. The effect of the intervention will be analyzed using multi-level modeling to adjust for clustering of participants at the facility level. We will use the daytime and nighttime average of lighting dosages (lux and CS) from the personal light monitors as the independent variable to analyze the effect of SABL on changes in CMAI, NPI, and ARS. Although not powered for a detailed analysis, we will explore the impact of participant characteristics (sex, age, race, ethnicity, ADRD stage, and daylight exposure) on the intervention effect by adding them as covariates to the regression model.

Aim 2

All data will initially be assessed using descriptive techniques to examine underlying assumptions and detect any violations. To assess the intervention fidelity, the lux and CS data measured via manual measurements will be analyzed using one sample t-tests to analyze lighting levels during the day and nighttime, compared to the target levels. The data from personal light monitors will be analyzed similarly at individual level. Although not powered for a detailed analysis, we will explore the impact of participant characteristics (e.g., sex, age, race, dementia stage, comorbidity, facility, and daylight conditions) on the lighting received based on the personal light monitor.

Aim 3

Quantitative Analysis: The data include ratings of acceptability, feasibility, appropriateness, time, and cost of installing and maintaining the intervention. All data will be analyzed using descriptive analyses. Although not powered for a detailed analysis, we will explore differences in perceptions of intervention feasibility and acceptability between sexes as well as the difference across professional roles and between facilities.

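### Light-monitor dose is likely to be missing more often in agitated resident-weeks, and Aim 1 has neither a model by assigned lighting phase nor a missing-dose method to keep those visits

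*Protocol*

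**What the plan says.** - **Exposure.** Protocol 8.3 and the SAP, in identical words: "We will use the daytime and nighttime average of lighting dosages (lux and CS) from the personal light monitors as the independent variable". Protocol 7.1 likewise says the effect on agitation, other BPSD, affect and sleep will be evaluated "based on the actual lighting levels participants receive measured by personal light monitors".
- **When the monitor is not placed.** Protocol 5.6.2.3, on residents who cannot consent, covers verbal or non-verbal resistance. If residents object or "push away the monitor, we will not proceed with the procedures and may approach the resident at a later time". Protocol 7.2.1 describes placement only for the willing: "For a resident who does not mind having the sensor placed on clothing, we may place it on the shirt collar or shoulder". It gives no alternative for the others.
- **What agitation is.** Protocol 2.1 describes it as disruptive behaviour, "such as screaming, wandering, resisting, grabbing, and hitting".
- **Outcomes.** Table 2 takes CMAI, NPI-NH, ARS and sleep from staff caregivers, covering the past week. They do not depend on the monitor.
- **Recovery of wear.** Protocol 7.2: "the light monitor will be worn 7 days a week during the data collection weeks". Protocol 7.2.1 adds site checks at least twice a week. Protocol 7.4.24 adds an automatic alert for apparent non-wear, and then: "We will make all attempts to check the device on site".
- **Not stated in either document.** A minimum wear time, a treatment of missing dose, or a model term for SABL, control or washout.

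**The concern.** The event that prevents measurement of the exposure is related to the outcome. When missingness of a regressor depends on the outcome, fitting only the complete records can bias the coefficient. If missingness depended only on lighting phase or on the dose itself, the main loss would be precision.

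The records at risk are ones whose outcome is known. In a trial that enrols residents for agitation and lists increased agitation as a possible risk (Protocol 10.0), the analysis should not depend on whether a resident tolerated a button that week. The hypothesis in Protocol 1.1 compares SABL with baseline and control periods. That comparison needs no monitor.

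The rule against placing the monitor on a resisting resident is not in question. The point is how the analysis handles its consequence.

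**Working it through.** **1. The plan's own figure.** Protocol 8.2 gives d = 0.53, alpha = 0.05, power 0.92, and 40 enrolled falling to 40 × 0.9 = 36. The within-person normal approximation is power = Φ(d√n − z).

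- n = 40, two-sided: Φ(3.352 − 1.960) = 0.918 (noncentral t: 0.905).
- n = 36, one-sided: Φ(3.180 − 1.645) = 0.938 (t: 0.930).
- n = 36, two-sided: Φ(3.180 − 1.960) = 0.889 (t: 0.871).

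The stated 0.92 therefore reproduces at 40 two-sided or 36 one-sided, but not at 36 two-sided. That is a separate matter; here 36 two-sided is the reference.

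**2. Loss of usable residents (illustrative, since no refusal rate is given).**

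| Residents without usable dose | Usable n | Two-sided t power |
|---|---|---|
| 0% | 36 | 0.87 |
| 10% | 32 | 0.83 |
| 20% | 29 | 0.79 |
| 30% | 25 | 0.72 |
| 40% | 22 | 0.66 |

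**3. Effect on the SABL-minus-control contrast.** All inputs are assumptions: CMAI mean 57, between-resident SD 8, within-resident SD 6, SABL effect −4.8. The chance of a missing dose follows a logistic curve through 5% at CMAI 47 and 20%, 35% or 50% at CMAI 67. The simulation used 400,000 residents. The contrast is the mean change from baseline at SABL visits with a dose minus the same at control visits with a dose, with baseline scores always kept.

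In the second scenario 15% of residents worsen by 8 points, so the true mean is 0.85 × (−4.8) + 0.15 × 8 = −2.88.

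| Missing at CMAI 67 | Uniform effect, true −4.80 | Error | 15% worsen, true −2.88 | Error |
|---|---|---|---|---|
| 20% | −4.71 | 1.9% too small | −3.03 | 5.2% too large |
| 35% | −4.58 | 4.6% too small | −3.15 | 9.4% too large |
| 50% | −4.47 | 6.9% too small | −3.22 | 11.8% too large |

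With the uniform effect, 9.0%, 13.0% and 16.8% of SABL visits lose their dose, and 12.4%, 19.4% and 25.7% of control visits. With the worsening subgroup, its share of the SABL visits kept falls from 15% to 13.5%, 11.8% and 10.5%.

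**4. The change from baseline under SABL depends on how baseline is handled.**

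| | True | Baseline score always kept | Baseline dose also required |
|---|---|---|---|
| Uniform effect | −4.8 | −5.1 to −5.5 | −4.7 to −4.5 |
| 15% worsen | −2.9 | −3.3 to −4.2 | −3.0 to −3.2 |

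The monitor is also used at baseline (Protocol 7.2, 7.2.1), so the right-hand column cannot be ruled out. With a uniform effect the sign of the error reverses.

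**5. A regression on dose, closer to 8.3.** Assumptions: 36 residents, 7 visits, true effect −0.53 SD, half the outcome variance between residents, within-resident regression on visits with a dose.

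- Missingness unrelated to agitation: −0.53 to −0.54.
- Missingness rising with current agitation: −0.51 to −0.47 with 10-15% of visits missing, −0.50 to −0.45 with 20-25%, and −0.49 to −0.43 with 37-38%.

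The error is 3% to 19% toward no effect. Visits without a dose were 0.9 to 1.4 SD more agitated than those kept.

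**The case against.** Several stronger readings are tempting, and the documents do not support them.

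- **That the most agitated visits will have no dose.** One refusal need not void a week. The resident may be approached again, the monitor reads every 10 minutes over seven days, staff are asked to re-clip it, and non-wear raises an alert. Partial weeks may be the commoner result.
- **That missingness follows directly from the outcome score.** Resisting is one of several behaviours that make up agitation. CMAI is a staff rating of a whole week, and pushing a researcher away at placement is a single event. A link is plausible, but its strength is unknown.
- **That such visits certainly drop out of every Aim 1 model.** Complete-case fitting is the usual default but is neither stated nor excluded. The multi-level sentence in 8.3 stands apart from the dose sentence and could be read as a model of condition. If instead one change score per resident is meant, a missing dose could cost the whole resident.
- **That improvement is exaggerated and worsening hidden.** Step 4 shows the exaggeration is not robust. The adverse-event checklist in Protocol 19.1.2 records deteriorated BPSD every two weeks without the monitor, and 18.2 compares symptoms in the SABL weeks with other periods.

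The simulations also rest on assumed values. The one in steps 3 and 4 ignores the CMAI entry threshold of about 45: with total SD √(64 + 36) = 10, Φ((45 − 57)/10) = Φ(−1.2), about 11% of its baseline scores, would be ineligible.

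What stands after all this is an outcome-related route to missing dose, a monitor-based exposure as the only one named, and no rule for its absence.

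**Conclusion.** The concern holds in a limited form. Agitated resident-weeks are more likely to lack a valid dose, and as written the plan could lose visits whose outcomes are known, selectively by outcome. In the scenarios tried, the error in the SABL-minus-control contrast is about 2-7% too small with a uniform effect and about 5-12% too large if a subgroup worsens. A dose regression erred 3-19% toward no effect. Neither the direction nor the size in the actual trial can be stated, because the documents give no refusal rate and no wear rule.

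Precision is also exposed: the 10% attrition allowance does not mention missing dose, so usable data could fall below 36 residents. This should be changed before analysis. Uncertainty about direction is itself a reason to fix the method in advance.

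**What to change.** In Protocol 8.3 and the SAP:

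1. Make the main Aim 1 model one of assigned lighting phase (SABL, control, washout) and period, fitted to all staff-rated visits whether or not a dose was recorded.
2. Keep measured dose as a second model, with a stated valid-wear rule that accepts partial weeks.
3. Multiply impute a missing dose from home, phase, visit, available on-site readings, the resident's monitor data from other weeks, and the outcome scores.
4. Add a sensitivity analysis for dose missing not at random.
5. Report monitor-missing visits by phase and by CMAI level.

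The cost is SAP text and some programming, with no added burden on residents. An imputed dose is less precise than a worn one. On-site readings can inform the imputation only where they were taken: the documents promise manual readings twice a week, but not at each resident's bed or seat.

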- 1) Surveys: Surveys will be administered to staff in-person and on paper to collect their characteristics (e.g., age, race, gender, education, & professional experiences) and their evaluation on the acceptability, feasibility, and appropriateness of the SABL lighting intervention.
- 2) Qualitative interviews: Staff's and administrators' inputs on the acceptability, feasibility, and appropriateness of the SABL lighting intervention.
- 3) We will also calculate the total hours and cost of installing and maintaining the SABL.

The procedures can be conducted either in person at the facility or via virtual conference (e.g., zoom). The procedure will be conducted in one visit scheduled in week 13.

Table 1. Intervention testing procedures and timeline.

Week		1	2	3	4	5	6	7	8	9	10	11	12	13
Study phases	NH A	Baseline	Intervention			Post intervention/washout			Control			Post control		
	NH B		Control			Post control/washout			Intervention			Post intervention		
Lighting		Usual light	I: SABL C: Usual light			Usual light			C: Usual light I: SABL			Usual light		
Data collection		Baseline, L&E		L&E		L&E		L&E		L&E		L&E		L&E

L=lighting measured via individual light monitor, E=effect outcomes (e.g., agitation, BPSD, affect, and sleep) and adverse effects

Table 2 Summary of Variables, Measures, and Data Collection.

Aim	Variables	Measures	Data collection methods	Timing
Aim 1	Facility characteristics	# of certified beds, ownership, quality rating, participation in Medicaid, staffing, COVID-related data.	CMS Medicare NH Compare Rating System.	Baseline.
	Resident characteristics	Age, race, sex, diagnoses, medication use, comorbidity, physical function, pain, vision, and dementia stage based on CDR.	Data extraction from medical records and MDS. CDR ratings will be measured via inputs from staff caregivers (e.g., nurse or CNAs).	
	Agitation, BPSD, affect, sleep & adverse effects	CMAI, NPI-NH, ARS, sleep & adverse events checklist.	Inputs from staff caregivers (e.g., nurse or CNAs) based on participants' conditions in past week.	Baseline & every two weeks.
Aims 1 & 2	Light level (lux & CS).	Lighting level each participant receives.	Personal light monitor, LYS button, every 10 minutes, 24 hours/day, 7 days/week.	
Aim 2	Light level (lux & CS).	Lighting level SABL delivers.	Manual on-site measurements.	Baseline & twice a week.
Aim 3	NH employee characteristics	Age, race, gender, education, & professional experiences.	Surveys.	Week 13.

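### Aim 1 explores who responds to SABL by adding covariates, which cannot separate a different SABL effect from a plain group difference in change

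*Protocol*

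**What the plan says.** Protocol section 8.3, Aim 1, names six characteristics to be explored: sex, age, race, ethnicity, stage of ADRD, and exposure to daylight. The same sentence gives both the target and the method, namely to look at their impact "on the intervention effect by adding them as covariates to the regression model". The SAP repeats this under Aim 1. The sentence opens with a caveat: "Although not powered for a detailed analysis".

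The regression it refers to is described just before. The baseline to post-intervention changes in CMAI, NPI-NH and ARS "scores will be used as the outcomes in all subsequent analyses". The light averages come "from the personal light monitors as the independent variable to analyze the effect of SABL on changes in CMAI, NPI, and ARS". The section also says that "each participant will serve as their own control, which allows minimal use of control variables", and that a multilevel model will handle clustering by facility.

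Neither document mentions an interaction, a product term, a moderation model or a stratified analysis for Aim 1.

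The resident characteristics in Table 2 (Protocol section 7.2) are "Age, race, sex, diagnoses, medication use, comorbidity, physical function, pain, vision, and dementia stage based on CDR". Ethnicity is not among them, nor in the chart-review list in 7.2 or the baseline-visit list in 7.2.1. No resident-level measure of daylight exposure is defined.

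**The concern.** The question is whether the SABL effect differs by characteristic. The method, read plainly, gives each characteristic a coefficient of its own beside the dose term. That coefficient says whether the average change differs between, say, men and women at the same dose. It does not say whether light works better in one sex than the other, because the model allows only one dose effect.

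Two errors are possible. A group whose agitation would have fallen more anyway could be reported as responding better to SABL. A real difference in response could be masked if a level difference runs the other way. Section 2.3 says the findings will inform the design of future studies, so a wrong statement about who benefits could shape the next trial's population.

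**Working it through.** **The plan's own figure.** The documents give no power or precision for this exploratory analysis. The nearest figure is the 0.92 for the main effect in section 8.2 ("This sample size was calculated based on a significance level of" 0.05, d = 0.53, 40 enrolled, 36 after 10% attrition). For a paired comparison, power is approximately Φ(d√n − z).
- n = 40, two-sided: Φ(0.53 × 6.325 − 1.960) = Φ(1.392) = 0.918, which reproduces 0.92.
- n = 36, two-sided: Φ(3.18 − 1.960) = 0.889, which does not.
- n = 36, one-sided: Φ(3.18 − 1.645) = 0.938, which is within two points.

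Sidedness is not stated. Nothing below depends on this figure.

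**What the covariate coefficient estimates.** Write the fitted model as change = a + b·dose + c·X, with X a 0/1 characteristic. By construction b is the same at X = 0 and X = 1. Suppose that the truth is

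change = a + b·dose + δ·X·dose + L·X,

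where dose is measured from the point at which light has no effect, δ is the true difference in dose effect, and L is a level difference unrelated to SABL. If dose is distributed alike in both groups with mean μ, the fitted c estimates approximately

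c ≈ L + δ·μ.

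The coefficient is the sum of the nuisance (L) and the target (δ·μ), and the model cannot split them. With μ = 0 it misses δ altogether. With μ > 0 it responds to δ, but a suitable L produces the same value, and L = −δμ cancels it.

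**Simulation.** All values are assumptions: 36 residents, one record each, X split 18/18, dose SD 1, residual SD 1, 4,000 runs per row, two-sided 5% test.

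| μ | δ | L | mean c | covariate significant | interaction significant |
|---|---|---|---|---|---|
| 0 | 1.0 | 0 | 0.01 | 5% | 77% |
| 0 | 0 | 1 | 1.00 | 81% | 5% |
| 1 | 1.0 | 0 | 1.00 | 73% | 77% |
| 1 | 0 | 1 | 0.99 | 81% | 4% |
| 1 | 1.0 | −1 | 0.02 | 5% | 76% |
| 1 | 0.5 | 0 | 0.50 | 29% | 28% |
| 1.5 | 1.0 | 0 | 1.49 | 97% | 76% |
| 1.5 | 0.5 | 0 | 0.75 | 56% | 28% |

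The mean of c follows L + δμ in every row. The interaction term responds to δ and ignores L.

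**Where μ might lie.** Section 7.4.6.3 gives usual bedroom light of 250 (±105) lux against a 400 lux target: (400 − 250)/105 = 1.4 SD. If that room-level SD is borrowed for personal dose, and usual light is taken as the no-effect point (both assumptions), μ is nearer 1 to 1.5 than 0. The rows with μ = 0 are then the less realistic ones.

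**Precision after the change.** Take a within-person contrast with SD of differences 1 and a balanced binary characteristic. The standard error of the subgroup difference is √(4/36) = 0.333 SD, so the 95% CI half-width is about 2.03 × 0.333 = 0.68 SD. Power for a subgroup difference of 0.53 SD is 0.34 at n = 36 (0.37 at n = 40). The smallest difference detectable with 80% power is about 0.97 SD (0.91 SD at n = 40).

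**The case against.** Four arguments deserve weight.

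**The covariate coefficient is not empty.** A reader might infer that the planned analysis says nothing about who benefits and would always miss real modification. The documents do not support that. The outcome is already a change score, and at a mean dose 1 SD above the no-effect point the covariate responds to real modification about as often as the interaction does (73% against 77%). Total blindness arises only when dose is centred at the no-effect point. The defect is non-specificity, and that stands.

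**Another model would make the covariate correct.** With one SABL-minus-control difference per resident and no dose or condition term, a covariate's coefficient is itself the interaction. Simulated with subgroup effects of 0 and −1.06, both forms gave −1.05. Since residents are their own controls and the model is not written out, this might be what is meant. But section 8.3 specifies change from baseline to post-intervention, with light dose as the predictor. That the covariates are main effects is an inference from the absence of any product term; it is the plain reading.

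**Daylight.** A reader might infer that entering daylight beside monitor dose splits the dose itself. Section 7.4.2 does say that daylight may take residents above target, so overlap is possible. But neither document defines daylight exposure as part of the monitor reading, and section 7.4.1 describes a separate digital model of indoor daylight. Only a request for a definition is justified.

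**The analysis is exploratory and declared unpowered.** This is true, and no main conclusion rests on it. It limits the importance of the point. It does not justify fitting a term that estimates something else.

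**Conclusion.** The point holds as a mismatch between question and method. As written in section 8.3 and the SAP, the model imposes one SABL effect on everyone and offers a coefficient that adds effect modification to any other group difference in change. A significant covariate could mean either, and a null one could mean that they cancel. In the illustrative case with μ = 1, the covariate was significant in 73%, 81% and 5% of runs under modification alone, a level difference alone, and the two offsetting. The interaction gave 77%, 4% and 76%.

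Those percentages rest on assumed effect sizes, a balanced binary characteristic and one record per resident, whereas the trial has seven data-collection visits and a multilevel model. They show direction, not the trial's operating characteristics. The algebra does not depend on them.

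The consequence is limited: one exploratory sentence in a 40-resident pilot. It is worth correcting because the correction is nearly free. The missing ethnicity variable is a minor list mismatch. A reader might infer that this analysis cannot be done, but race already comes from the chart and MDS review, and adding ethnicity to the extraction form is a clerical step.

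**What to change.** In Protocol section 8.3 and the SAP, Aim 1, replace the phrase about adding covariates with: adding each characteristic and its interaction with light dose (or with SABL versus control condition), one characteristic at a time. Report each interaction estimate with its 95% CI, labelled exploratory.

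Two smaller edits:
- Add ethnicity to the baseline extraction (section 7.2, Table 2 and 7.2.1), or drop it from the list of modifiers.
- Define daylight exposure, with its source and unit of measurement, so that it is distinct from total monitor dose before it is used as a modifier.

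The cost is one sentence in each document, one extra model term per characteristic and, if ethnicity is kept, one more extracted variable. The downside is wide intervals (about ±0.68 SD under the assumptions above), which the plan's caveat on power already accepts.
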